The main objective of this study is to evaluate the feasibility of using TOMs in the assessment of OH-associated postural stability, both “in-clinic” and “at-home”. Twelve consecutive PD patients with OH about to start pharmacological treatment with vasopressor agents prescribed by their neurologist will undergo gait and postural assessments (Protokinetic Zeno Walkway) before and after treatment with vasopressor agents (Droxidopa). Patients will also use wearable motion sensors (WMS) (Apple Watch® - Apple, Cupertino, CA, USA) for monitoring their normal activities of daily living. Gait analysis will measure the improvement in stride length and velocity, double-support time (percentage of time spent with both feet in contact with the ground), and postural sway on the anteroposterior and lateral axis, both at baseline (before treatment with Droxidopa) and after 6 weeks of therapy (2 weeks of dose-titration plus 4 weeks of maintenance therapy). Data collected by TOMs (a) before and (b) after treatment with Droxidopa, will be correlated with changes in conventional scales of postural stability (Tinetti balance scale) [10], OH questionnaire (OHQ) [7], quality of life measures (39-Item Parkinson's disease questionnaire, PDQ-39)[11], and cognitive functions (Cambridge neuropsychological test automated battery – CANTAB - Connect Research, Cambridge Cognition Ltd., UK - and CERAD-NAB).[12, 13]

Our **central hypothesis** is that TOMs will result in higher detection power and lower variability than conventional clinical assessments, also minimizing interferences due to the placebo effect. If confirmed, these findings will improve the treatment in PD by using TOMs, instead of standard subjective outcome measures.

AIMS OF THE STUDY

The two aims of this study are:

Aim #1: To evaluate the feasibility and effect-size of using gait and postural tests to quantify OH related postural stability during in-clinic evaluations:

PD patients with newly diagnosed OH (n = 12) will be assessed at baseline and after 1 month of anti-OH treatment with the following tests:

Clinical tests: OHQ score (OH Symptom Assessment, OHSA and Orthostatic Hypotension Daily Activities Scale, OHDAS), Tinetti score, PDQ-39 score.

Gait analysis: stride length, single leg stance time, dynamic stability index, and gait velocity

Postural analysis: postural sway on the X and Y-axis.

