Hypothesis: Gait analysis and Postural analysis will accurately capture changes in gait and postural stability associated with OH treatment, with higher sensitivity and lower variability than standard clinical tests.

Aim #2 To evaluate the feasibility and calculate the effect size of using WMS to quantify OH related postural instability during at-home activities of daily living

Gait and postural stability will be evaluated in the home environment by means of the following outcome measures:

Clinical assessment: Self-assessed clinical diary (OHDAS-based score) evaluating the subjective sensation of postural instability and number of episodes of postural instability.

WMS assessment: WMS (Apple Watch®) evaluating functional parameters, namely a) number of steps per day; b) number of hours of standing per day; c) total calories and active calories per day.

Hypothesis: TOMs will provide an accurate measure of functional parameters in the home setting, thus allowing an indirect measure of the patients' quality of life, with higher sensitivity and lower variability than self-reported clinical diaries.

INVESTIGATOR EXPERIENCE: Please see attached Bio sketch.

CLINICAL EVALUATIONS

Screening Assessment (Day 0)

12 consecutively consenting PD patients with OH about to start pharmacological treatment with a vasopressor agent (Droxidopa), as prescribed by their treating physician from the Gardner Family Center for Parkinson's Disease and Movement Disorders, will be screened for the following inclusion/exclusion criteria:

Inclusion criteria: (a) Diagnosis of idiopathic PD, meeting UK Brain Bank criteria [15] for at least 3 years; (b) Hoehn and Yahr (H&Y) stage I-III; (c) Age between 30 and 80 years old (both inclusive); (d) Stable dosage of dopaminergic medications for at least 4 weeks; (e) OH, defined as a fall in systolic BP \geq 20 mmHg or diastolic BP \geq 10 mmHg within 3 minutes of standing [16]; (f) Willingness and ability to comply with scheduled visits.

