Data will be described with appropriate summary measures (mean and SD, or median and interquartile range) at Visit 1 (before Droxidopa treatment) and Visit 3 (after 4 weeks of Droxidopa maintenance therapy). Changes in the main clinical (PDQ-39, Tinetti, OHQ and related subscales), gait (stride length, single leg stance time, dynamic stability index, and gait velocity) and postural (postural sway on the X and Y axis) outcomes will be compared between Visit 1 and Visit 3 using the paired t-test/ non parametric Wilcoxon signed rank test depending on the distribution of change outcome. Effect size (mean or median change and percent change) will be reported along with 95% confidence interval (CI). In addition, data collected with TOMs before and after treatment with Droxidopa will be correlated with changes in the PDQ-39, OHQ, CANTAB and CERAD-NAB by means of the Pearson correlation/Spearman rank correlation analysis.

Hypothesis: Gait analysis and Postural analysis will accurately capture changes in gait and postural stability associated with OH treatment, with higher sensitivity and lower variability than standard clinical tests.

Aim #2 To evaluate the feasibility and calculate the effect size of using WMS to quantify OH related functional parameters during at-home activities of daily living

Postural data collected from WMS (Apple Watch®) and evaluating: (1) Number of steps per day; (2) number of hours of standing per day; and (3) total calories and active calories per day, will be analyzed and compared with episodes of subjective (OHDAS-based diary) postural instability recorded during the follow-up period using a paired t-test/Wilcoxon signed rank test. In addition, we would also evaluate the changes from pre-baseline to post baseline of subjective measure of postural stability and correlate with objective measures of postural stability using Pearson correlation/Spearman rank correlation analysis. Statistical analyses will be carried out using SAS 9.3.

Hypothesis: WMS will provide an accurate measure of functional parameters in the home setting, thus allowing an indirect measure of the patients' quality of life, with higher sensitivity and lower variability than self-reported clinical diaries.

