Missing data on the scores will be handled by a two-step approach. Less than 20% missing data on any variable for an individual will be imputed using the mean of the final score of that question. Greater than 20% missing data for any participant on any instrument will be handled by a multiple missing imputation approach. Missing data on BP related variables will be imputed using multiple missing imputation approach.

Sample Size Calculation: Given the exploratory nature of this pilot study, the sample size calculation is inevitably limited by the lack of previous data. We used a study analyzing the effect of levodopa in PD with

a gait analysis [21], which reported a 30% improvement in the stride length (SD 31.3%), to pre-specify a threshold of minimal improvement of 10% between baseline and follow-up. With these assumptions, we estimate that a sample of 12 patients will be more than sufficient to detect significant differences using a paired t-test, with more than 80% power and at 5% level of significance (PASS 14 Power Analysis and Sample Size Software (2015). NCSS, LLC. Kaysville, Utah, USA, ncss.com/software/pass).

Innovation

Although TOMs are unanimously thought to represent the future of medical assessments, their routine application is limited by the lack of validation studies proving their efficacy and reliability in clinical trials. The current proposal will provide more sensitive standards for the assessment of OH complications in PD, with the main innovation of developing and validating an innovative outcome measure based on a mobile (WMS) and in-clinic (gait analysis) technology.

DATA STORAGE AND CONFIDENTIALITY:

All records from this study will be maintained in a secure setting. We will be using REDCap (Research Electronic Data Capture) as the secure web-based application to store data for this research study. Records will not have any patient health information (PHI) associated with them. These records will be kept indefinitely to allow for re-analysis of data, if needed. The data will never be accessible without a secure password.

RISKS AND BENEFITS:

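### Aim 1 claims that TOMs are more sensitive and less variable than clinical tests, but the planned analysis never compares the two, and its effect size ignores the variability of change

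*Combined protocol and SAP*

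**What the plan says.** **The claim.** Experimental Design and Patient Population gives the central hypothesis: "TOMs will result in higher detection power and lower variability than conventional clinical assessments". The Aim #1 hypothesis, under Aims of the Study and again under Data Analysis, says that gait and postural analysis will capture treatment-related change "with higher sensitivity and lower variability than standard clinical tests". Experimental Design and Risks and Benefits both look ahead to TOMs replacing subjective measures.

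**The analysis.** Data Analysis, Aim #1 specifies four things:

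- Summaries at each visit: "Data will be described with appropriate summary measures (mean and SD, or median and interquartile range) at Visit 1" and again at Visit 3.
- A test within each instrument, for clinical, gait and postural measures alike: these "will be compared between Visit 1 and Visit 3 using the paired t-test/ non parametric Wilcoxon signed rank test". The choice between the two tests rests on how the change is distributed.
- An effect size for each outcome: "Effect size (mean or median change and percent change) will be reported along with 95% confidence interval (CI").
- Correlation. TOM data "will be correlated with changes in the PDQ-39, OHQ, CANTAB and CERAD-NAB by means of the Pearson correlation/Spearman rank correlation analysis".

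**The sample size.** It concerns stride length alone: "we estimate that a sample of 12 patients will be more than sufficient to detect significant differences using a paired t-test". The power claimed is above 80%, at a 5% significance level.

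**The concern.** More sensitive and less variable are statements about one instrument relative to another. None of the four planned steps sets a TOM beside a scale on responsiveness. A paired test asks whether one instrument moved. A correlation asks whether two instruments move together, and two measures can correlate well while one detects change far better than the other. Neither sensitivity nor variability is given an operational definition.

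The stated effect size does not fill the gap. Raw change is in the units of each instrument. Percent change has no units, but it depends on where each instrument's zero lies, and it leaves out the SD of change. That SD is what decides how many patients are needed to detect a given change.

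The study is titled as an effect-size finding study, and Future Directions says it will inform a larger proposal. If the plan is followed as written, its main scientific claim goes unaddressed. Any comparison would then be chosen after the data are seen, from several TOMs and several scales.

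**Working it through.** **1. The plan's own figure.** Inputs from Sample Size Calculation: n = 12, a 30% improvement in stride length, SD 31.3%, and 5% significance (taken as two-sided). The 31.3% is read here as the SD of change. The standardised effect is 30 / 31.3 = 0.96. Exact noncentral-t power for a paired test is 85.5%, and 11 patients give 80%, so 12 patients with more than 80% power reproduces. With the 10% threshold named in the same paragraph, the effect is 10 / 31.3 = 0.32, power is 17.3%, and 79 patients are needed. That discrepancy is a separate matter. What counts here is that both calculations set stride length against its own baseline, and neither concerns a TOM against a scale.

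**2. Why the SRM matches the claim.** SRM = mean change / SD of change, and the paired t statistic is SRM × √n. The SRM therefore measures detection power directly. Its inverse, SD of change / mean change, is variability relative to the change.

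**3. What the stated metric misses.** Take two instruments with the same 10% mean change at n = 12. One has the plan's SD of 31.3%; the other has an assumed SD of 10%. CI half-width = 2.201 × SD / √12.

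| SD of change | Percent change (95% CI) | SRM | t |
|---|---|---|---|
| 10% (assumed) | 10 (3.6 to 16.4) | 1.00 | 3.46 |
| 31.3% (plan) | 10 (-9.9 to 29.9) | 0.32 | 1.11 |

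The point effect sizes are equal, although one instrument is about three times as responsive (31.3 / 10 = 3.13).

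**4. Comparing p-values does not repair it.** In 40,000 simulated trials of 12 patients with two equally responsive instruments (correlation 0.3 between their changes), exactly one was significant in 39% of trials when both SRMs were 0.5, and in 35% when both were 0.8.

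**5. What can be recovered afterwards.** For an outcome reported as a mean with a t-based CI, SD of change = half-width × √12 / 2.201. For the second row, 19.9 × 3.464 / 2.201 = 31.3. This does not work for outcomes reported as medians. A CI for a paired difference in SRM also needs the correlation r between the two change scores, which separate tables do not give.

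**6. What the comparison would deliver at n = 12.** Exact 95% CIs for a single SRM are 0.32 (-0.27 to 0.89), 0.50 (-0.11 to 1.09) and 0.96 (0.25 to 1.63). For the difference between SRMs g1 and g2 in the same patients:

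var = [2 - 2r + (g1² + g2²)/2 - r² × g1 × g2] / n

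Take g1 = 0.958 (the plan's 30 / 31.3) and g2 = 0.5. The documents give neither g2 nor r, so both are assumed. The difference is 0.46.

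| r | SE | 95% CI | Power | n for 80% |
|---|---|---|---|---|
| 0 | √(2.584/12) = 0.464 | -0.45 to 1.37 | 17% | 97 |
| 0.3 | √(1.941/12) = 0.402 | -0.33 to 1.25 | 21% | 73 |
| 0.7 | √(0.949/12) = 0.281 | -0.09 to 1.01 | 37% | 36 |

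The formula is a large-sample one. In simulation with equal SRMs the corresponding test rejected in about 7% of trials against a nominal 5%, so the true intervals are somewhat wider.

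**The case against.** The strongest reply is that this is a pilot with feasibility as its main objective, described in Sample Size Calculation as exploratory, and that its tables contain more than point estimates. The SD at each visit, the paired test and the CI would all be there, and a reader who sees a narrow interval for stride length and a wide one for a scale would draw the right lesson. Mean change over the Visit 1 SD could also be computed from those tables. This stands in part: the gap lies in what is pre-specified, not in the data. It does not remove the point, because the comparison is the stated hypothesis, medians are allowed, and the paired difference cannot be rebuilt from the tables.

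A second reply is that 12 patients cannot settle the comparison under any metric. That is correct, and it limits the remedy to estimation.

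Two stronger readings are tempting, and the documents do not support them.

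- A reader might infer that percent change would rank the instruments in the wrong order. That depends on inputs the plan does not give. With an invented 0-10 scale and an assumed 10% SD of change for stride length, the SRM favours stride length in 90% of simulated trials. With the plan's 31.3% it does so in 42%, and the contradiction between the two metrics disappears.
- A reader might infer that percent change will often be undefined because symptom-free patients score 0 at baseline. Patients must also be about to start prescribed droxidopa, and the Background says that many without classic symptoms report others. No frequency of zero scores is given, and the plan does not say that percent change is computed patient by patient.

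**Conclusion.** The point holds as a gap between hypothesis and analysis. Followed as written, the Aim 1 analysis does not address whether TOMs are more sensitive or less variable than clinical tests, and the effect size it defines leaves out the variability of change. That conclusion rests on the text alone.

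It does not follow that the effect sizes cannot be compared at all, that the data could not support the comparison, or that the planned tables would mislead. Percent change is unit-free, and the SRM is recoverable for outcomes reported as means with t-based CIs.

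The size of the remaining uncertainty depends on an assumed clinical SRM of 0.5 and an assumed correlation. Across r = 0 to 0.7, the interval for a difference of 0.46 includes zero throughout. Even a properly specified comparison at n = 12 can only estimate, and the hypothesis should not be worded as something the study will prove. The change should be made, but it does not threaten the feasibility objective.

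**What to change.** In Data Analysis, Aim #1:

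- For every TOM and every clinical scale, report the SD of change and the SRM, signed so that positive means improvement, with a 95% CI, whichever paired test is used.
- Add the within-patient difference in SRM between stride length (the sample-size measure) and the OHQ and Tinetti scores, with a CI from bootstrap resampling of patients. Give the same differences for the other gait measures, sway and PDQ-39 as secondary.
- Keep raw change as description. Do not use percent change to compare instruments.
- Define sensitivity and variability in these terms, state that the comparison is estimation and not a test, and soften the hypothesis wording wherever it appears.
- When interpreting OHQ responsiveness, note that OHQ item 1 forms part of one criterion in the Droxidopa Titration Plan. The instrument being compared therefore also helps to steer treatment.

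The cost is SAP wording and a few lines of code. No new data are needed, provided that the Tinetti score is collected at both visits: Aim #1 and Data Analysis name it, but the Clinical Assessments list for Visit 1 does not, so that list should be checked. The drawback is that the intervals will be wide and the result will read as an estimate.

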Title of the Study: Technology-Based Objective Measures for Gait and Postural Assessment in Parkinson Disease Patients with Orthostatic Hypotension: Feasibility and Effect-Size Finding Study.

Principal Investigator: [name], MSc

Funding: Investigator-initiated study sponsored by Lundbeck

BACKGROUND:

Neurogenic orthostatic hypotension (OH) is a frequent and disabling complication of Parkinson's disease (PD), with an estimated prevalence of 30-50% [1-3], and a significant impact on the quality of life (QoL). OH may be associated with potentially serious complications, such as postural instability, gait impairment, and falls, which directly or indirectly (e.g., fractures) represent the most frequent cause of hospitalization in PD [4-6].

The lack of objective measures for the assessment of OH disability, however, represents a clinical challenge in the management of this complex hemodynamic condition. Although different scales have been developed for the assessment of orthostatic intolerance in PD [7], their application is limited by the substantial proportion of patients not reporting "classic" OH symptoms, namely dizziness, lightheadedness, or "feeling like you might black out while standing" [7]. Up to 50% of OH patients may complain symptoms such as weakness, vertigo, and difficulty concentrating, which may be erroneously diagnosed, underestimated, and thus undertreated. In a recent study, we demonstrated that OH might cause a 3-fold risk of gait impairment and functional disability in PD, regardless of the presence/absence of postural lightheadedness [8].

Clinical assessment and monitoring of OH symptoms relies on inaccurate and highly subjective clinical measures based on quantification of symptoms that are frequently ambiguous and not specific. In a recent study where we assessed the impact of autonomic dysfunction in 121 consecutive PD patients, OH was independently associated with gait impairment and functional disability, regardless of the symptomatic or asymptomatic status [8]. These data support the hypothesis that clinical scales currently available for quantifying the severity of OH are not adequate for capturing the full complexity of this frequent yet under-recognized PD complication.

Technology-Based Objective Measures (TOMs)

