Clinical Assessments: Motor severity as per the MDS-Unified Parkinson's Disease Rating Scale (MDS UPDRS) [20]; OH symptoms severity as per the full OHQ (OHSA and OHDAS) scale [7]; quality of life as per the PD questionnaire (PDQ-39) [11]; Cognitive assessment as per the Cambridge automated neuropsychological test battery (CANTAB) [12] and CERAD-NAB [13].

Clinical Diary: Patient will be instructed to score the severity of the OH-related episodes of postural instability and the number of episodes of postural instability a day before starting titration with droxidopa, 1 day after V2 and 1 day after V3; using a self-assessed clinical diary based on the OHDAS (a section of the OHQ assessing the impact of OH symptoms on standing and walking).

Gait Assessments (average of two measurements): In order to evaluate variables of interest (stride length, single leg stance time, dynamic stability index, and gait velocity), patients will be assessed walking on the 20 feet-Protokinetics Zeno Walkway. Patients will be instructed to "walk from the mark (red tape) before the mat to the mark after the mat, turn around and walk back". After a preliminary review for acquisition errors, the data will downloaded into a Matlab-based software platform prepared ad-hoc for this study (Matlab, Mathworks, CA, USA) by the Department of Bioengineering of the University of Cincinnati ([name]).

Postural Assessments (average of two measurements): In order to evaluate variables of interest (postural sway on the X and Y-axis, as measured by the center of mass estimated X and Y range), patients will be asked to perform a modified Clinical Test of Sensory Interaction on Balance. Patients will stand on the mat for 30 seconds under the 2 following conditions: eyes open/rest and eyes closed/rest, with their feet 1"-2" apart and arms at their side. For the eyes open condition, he/she will be asked to focus on a point in front of him/her at eye level to control for visual distractions. Data will be collected and stored into the software platform described above.

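### Aim 2 tests watch steps, hours and calories against diary episodes as if they were paired like quantities, and specifies no before-after change for any watch variable

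*Combined protocol and SAP*

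**What the plan says.** The title describes a "Feasibility and Effect-Size Finding Study", and Aim #2 in Aims of the Study is "To evaluate the feasibility and calculate the effect size of using WMS to quantify OH related postural instability". The Aim #2 part of Data Analysis then gives two analyses.

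- **First analysis.** Steps, standing hours, and total and active calories per day are to be "compared with episodes of subjective (OHDAS-based diary) postural instability recorded during the follow-up period using a paired t-test/Wilcoxon signed rank test".
- **Second analysis.** "we would also evaluate the changes from pre-baseline to post baseline of subjective measure of postural stability", and this is to be correlated with the objective measures.

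The paragraph closes with the hypothesis that the watch will measure function "with higher sensitivity and lower variability than self-reported clinical diaries".

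The plan's definition of effect size is in the Aim #1 paragraph: "Effect size (mean or median change and percent change) will be reported along with 95% confidence interval (CI"). The outcomes listed there for the Visit 1 to Visit 3 comparison are clinical scales, gait variables and postural sway. Experimental Design and Patient Population adds that "Data collected by TOMs (a) before and (b) after treatment with Droxidopa, will be correlated with changes in conventional scales".

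On data capture, the Droxidopa Titration Plan provides 2 days of baseline data collection before the drug starts. The diary is completed "a day before starting titration with droxidopa, 1 day after V2 and 1 day after V3".

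**The concern.** There are two linked faults.

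1. **The named test does not fit the data.** A paired t-test or signed rank test needs two measurements of the same quantity. A daily step count and a number of instability episodes are different quantities in different units, so their difference has no interpretation. The comparison is also confined to the follow-up period and so contains no before-after contrast.
2. **The estimate that Aim #2 calls for is not specified.** The only change analysis under Aim #2 is for the subjective measure. The text on technology data before and after treatment leads to a correlation, which is not the effect size the plan defines.

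The study's stated output is effect sizes to inform a larger proposal. Followed literally, the plan yields uninterpretable p-values for the watch and no watch effect size. The hypothesis of better sensitivity and lower variability than the diary also has no analysis attached. The feasibility part of Aim #2 is not affected, because hours of watch wear are counted.

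**Working it through.** The plan states no figure for any watch variable, so there is nothing of its own to reproduce. The first fault follows from the form of the test. The simulations show its size under assumed inputs.

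**Form of the test.** With X the watch value, Y the diary episodes and n = 12, the statistic is t = mean(X − Y) / [SD(X − Y)/√12]. Multiplying X by a constant c, which is only a change of unit, replaces X − Y by cX − Y. That is a different hypothesis. For two measurements in the same unit, rescaling both leaves t unchanged.

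**Inputs.** From the documents: 12 patients, a paired t-test and the 5% level (Sample Size Calculation). Two-sided testing is assumed. The documents give no watch or diary means, so these are also assumed: X normal, floored at 0; Y Poisson with mean 1, 2, 3 or 4; X and Y independent; no treatment effect; 20,000 simulated trials per setting.

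| Watch variable, mean (SD) | Unit | Diary mean 1 | 2 | 3 | 4 |
|---|---|---|---|---|---|
| Steps 4,000 (2,000) | single steps | 100% | 100% | 100% | 100% |
| Steps 4,000 (2,000) | thousands | 99% | 74% | 24% | 5% |
| Steps 2,000 (1,000) | thousands | 62% | 5% | 33% | 83% |
| Steps 6,000 (3,000) | thousands | 100% | 98% | 80% | 44% |
| Standing 6 h (3 h) | hours | 100% | 98% | 80% | 44% |
| Standing 6 h (3 h) | minutes | 100% | 100% | 100% | 100% |

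The entries are rejection rates. Within a column, the first two rows differ only in unit.

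**Response to treatment.** Follow-up steps = baseline × (1 + effect) + normal noise with an assumed SD of 1,000.

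| True change in steps | Watch against diary, single steps | Before-after on the watch |
|---|---|---|
| 0% | 100% | 5% |
| +10% | 100% | 24% |
| +30% | 100% | 91% |

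The planned test cannot tell these cases apart; the before-after test can.

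**Whether a watch change is specified elsewhere.**

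- Data Analysis, Aim #1: change, percent change and CI are given, but no watch variable is listed.
- Data Analysis, Aim #2: change is given for the subjective measure only.
- Experimental Design: technology data before and after treatment, leading to a correlation.

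No section asks for a before-after estimate of steps, standing hours or calories.

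**Precision of the missing estimate.** Assume 2 baseline days, 7 on-treatment days, mean 4,000 steps, and the same true change in every patient. Then SD of change = CV × 4,000 × √(1/2 + 1/7) = CV × 4,000 × 0.802. The 95% CI half-width = 2.201 × SD/√12 = 0.635 × SD.

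- Day-to-day CV 20%: 0.635 × 641 = 408 steps, about 10% of the mean.
- CV 30%: 0.635 × 962 = 611 steps, about 15%.
- CV 50%: 0.635 × 1,604 = 1,019 steps, about 25%.

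If the true change also varies between patients with an SD of 20 or 30 percentage points, the CV 20% half-width becomes 0.635 × √(0.2² × 0.643 + 0.2²) = 16%, or 0.635 × √(0.2² × 0.643 + 0.3²) = 22%.

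**The case against.** The strongest reply is that the sentence is compressed. The authors may have meant a before-after test within each measure plus a comparison with the diary. The Aim #2 heading asks for an effect size, the definition stands one paragraph earlier, and the design text calls for technology data at both times, so a reader could carry the definition over. That may well be the intent. But the sentence names diary episodes in the follow-up period as the comparator, and no sentence applies the definition to the watch. If this was the intent, the text still needs the correction.

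Three further points have some force.

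- **Assumed inputs.** All means, SDs and rates are assumed. The documents already express the variables as step counts and hours, so a change of unit is artificial, and calories are not in the tables. The tables are illustrations; the argument from unlike quantities does not need them.
- **Optimistic before-after figures.** They assume the same proportional response in every patient. Adding between-patient SDs of 20 or 30 percentage points lowers 91% to about 75% or 59%, and 24% to about 15% or 12%. That limits what the replacement can show but does not rescue the planned test.
- **Small exploratory pilot.** No primary decision rests on the watch p-value, and the data to compute the change appear to be collected. This makes the repair easy. It does not excuse leaving out an estimate that is one of the study's stated outputs.

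**Conclusion.** The concern holds, with high confidence as to the written text, and must be fixed. The first-listed Aim #2 analysis is invalid as written, and the effect-size part of Aim #2 has no analysis that delivers it. The size of the fault in the test depends on assumed values: across the settings tried, with no treatment effect, rejection ran from 5% to 100% according to unit and episode rate alone. That no watch change is specified depends on no assumption. The Aim #2 correlation and the feasibility part remain usable. The repair assumes that the watch is worn on both baseline days, which the documents suggest but do not state.

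**What to change.** 1. Delete the paired test of watch values against diary episodes.
2. For each watch variable, compute the within-patient change from the 2 baseline days before droxidopa to a pre-specified on-treatment window, for example the last 7 complete watch days before Visit 3. Test it by paired t-test or Wilcoxon, and report mean or median change and percent change with 95% CI, as for Aim #1. State that the watch is worn on both baseline days.
3. Relate watch to diary only by correlating their changes.
4. For the sensitivity and variability hypothesis, report a unit-free standardized change (mean change divided by SD of change, signed so that improvement is positive) with 95% CI, for each watch variable and for the diary score. Treat it as descriptive: with 12 patients, an observed value of 0.5 has a 95% CI of about −0.11 to 1.09 (noncentral t).
5. State which watch days are matched to each diary day. The last diary day falls after Visit 3, and the documents do not say whether the watch is still worn then. Either say that it is, or name the earlier watch window used for the correlation.

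Items 1 to 3 are the core. Items 4 and 5 are useful but separable, and other windows or indices could serve. Items 1 to 4 are mainly SAP wording on data the study appears to collect already. Item 5 needs one procedural sentence, and wearing the watch through the day after Visit 3 would be a new explicit instruction. No visit is added. The downside is the short baseline, whose imprecision should be stated with the results.
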